3. GENERAL CHARACTERISTICS ANALYSES

3.1 PARTICIPANT DISPOSITION

Participant disposition will be presented for the ROL analysis set, unless mentioned otherwise. The following participant data will be tabulated:

- The number of participants in each PAS .
- The number of participants with 1 treatment period and with 2 treatment periods respectively in the SAF analysis set.
- Descriptive statistics of each phase duration, calculated as phase end date – phase start date + 1 day.
- Descriptive statistics of each period and subperiod duration in the SAF analysis set, calculated as (sub)period end date – (sub)period start date + 1 day.
- The number and percentage of participants who completed or discontinued the treatment as documented on the treatment termination page and the number and percentage of participants for each treatment discontinuation reason. This table will be presented for the SAF analysis set
- The number and percentage of participants who completed or discontinued the study as documented on the study termination page and the number and percentage of participants for each study discontinuation reason.
- The number and percentage of participants with protocol deviations, by important/non-important deviations, and by class of deviation.

Listings will be created for:

- Indication of analysis sets in which a participant is included.
- All information collected in the CRF concerning study and treatment discontinuation.
- Visits (scheduled and unscheduled) performed by the participant, with visit date and indication whether the visit occurred at site or at home.
- Protocol deviations.

3.2 DEMOGRAPHIC AND OTHER BASELINE CHARACTERISTICS

3.2.1 *Available data*

The following parameters will be available:

- Demographics: sex at study start, childbearing potential, year of birth, age at informed consent, race, ethnicity, height, body weight and BMI at study baseline, date of signing ICF
- Baseline disease characteristics: disease status at study baseline (no CDA, CDA, CR, PR, Relapse, Treatment failure), BPDAl activity and total score at study baseline, IGA-BP at study baseline, itch NRS 24-hour average and worst score at study baseline

	Statistical Analysis Plan	
ARGX-113-2010	Final analysis	Final 1.0 of 29APR2025

- Study entry status: date of protocol version at entry, participant receiving rescue therapy at study baseline (yes, no), type of rescue therapy at study baseline (ATC class level 3), participant receiving OCS at study baseline (yes, no), and if yes, OCS dose at study baseline (mg) and OCS dose per body weight at study baseline (mg/kg)

3.2.2 *Derivation rules*

The following parameters will be derived:

- Age at informed consent, categorized (18 - <65, 65 - <75, 75 - <85, >=85)
- Height: if height is not available in the database of ARGX-113-2010, the height at screening of ARGX-113-2009 will be taken.
- BMI at study baseline (kg/m²) = (body weight (kg) at study baseline) / (height (m))².
- BMI at study baseline, categorized (Underweight: < 18.5 kg/m², Normal weight: 18.5 -< 25 kg/m², Overweight: 25 -< 30 kg/m², Obese: >= 30 kg/m²)
- Race, categorized (Asian, Black or African American, White, Other)
- Geographical region: Asia (Japan, China), North America (US, Canada), EU region+UK (EU/EEA/EFTA/UK), Rest of world
- BPDAl activity score at study baseline, categorized: <20, 20-56, >56
- OCS at study baseline: any use of systemic OCS on study day 1, i.e.. any record from any eCRF page with medication class = 'GLUCOCORTICOIDs' and route = 'ORAL' for which the available information indicates that the medication is taken on study day 1.
- Rescue therapy at study baseline: any use of therapy that is indicated as rescue therapy by the investigator on the eCRF page and for which the available information indicates that the medication is taken on study day 1.

3.2.3 *Presentation of results*

Demographics will be presented using descriptive statistics for age at informed consent, height, weight and BMI at study baseline and frequency tabulations for age category, BMI category, sex at study start, childbearing potential, geographical region, race category and ethnicity.

Baseline disease characteristics and study entry status will be presented using descriptive statistics for BPDAl activity and total score at study baseline, itch NRS 24-hour average and worst score at study baseline, OCS dose and OCS dose per body weight at study baseline and frequency tabulations for all other parameters.

All demographic data and baseline disease characteristics will be listed.

Displays will be based on the ROL analysis set.

3.3 **CONCOMITANT THERAPIES AND PROCEDURES**

3.3.1 *Available data*

All therapies are coded using World Health Organization Drug Dictionary (WHO DD). Anatomical-Therapeutic-Chemical (ATC) selection is performed to select the

	Statistical Analysis Plan	
ARGX-113-2010	Final analysis	Final 1.0 of 29APR2025

most appropriate medication class. For the selected class, ATC coding up to level 4 is available in the clinical database. For each therapy, a start and stop date are collected.

Procedures are coded using the medical dictionary for regulatory activities (MedDRA) into preferred terms. For each finding, the indication and a start and stop date are collected.

3.3.2 Derivation rules

Based on their start and stop dates, therapies and procedures will be allocated to each phase, period and subperiod during which the participant received the therapy.

Therapies/procedures with (partially) missing dates will be allocated to each possible phase/(sub)period unless the available parts of the therapy/procedure start or stop date provide evidence not to do so.

Concomitant therapies/procedures are therapies/procedures for which the available information indicates that the therapy/procedure is taken/performed on or after study day 1. In case of doubt (e.g. partially missing dates), it will be assumed that the therapy/procedure is concomitant.

OCS therapy is defined as any record from any eCRF page with medication class = 'GLUCOCORTICOIDS' and route = 'ORAL'.

TCS therapy is defined as any record from any eCRF page where medication class contains 'CORTICOSTEROIDS' and route = 'TOPICAL'.

Rescue therapy is defined as any therapy that is indicated as rescue therapy by the investigator on the eCRF page.

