6.9. Prior and Concomitant Therapy

Any medication or vaccine (including over-the-counter or prescription medicines, recreational drugs, vitamins, and/or herbal supplements [including Chinese traditional medicine]) or other specific categories of interest that the participant is receiving at baseline or during the study must be recorded and include the following information:

- Reason for use
- Dates of administration, including start and end dates
- Dosage information (ie, dose and frequency)
- Brand name (for vaccines only)

The following medications or treatments are not permitted as of when the ICF has been signed through the completion of the EoTP visit or EDV, as applicable:

- SC immunoglobulin

- IV immunoglobulin unless initiated as rescue therapy in ARGX-113-2009 (refer to Section 6.9.2)
- Plasma exchange
- Immunoabsorption
- Monoclonal antibodies:
 - Rituximab
 - Other anti-CD20 biologics
 - Other monoclonal antibodies
- Sulfasalazine
- Any systemic treatment for BP (eg, IV or intramuscular corticosteroids, systemic immunosuppressants) except OCS
- Complementary therapies, including traditional Chinese medicines, herbs, or procedures (eg, acupuncture) that may interfere with the study's efficacy assessments and/or potentially risk the safety of the participant
- Live or live-attenuated vaccines
- Any other systemic biologic agent or experimental/study IMP

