4. EFFICACY, PHARMACODYNAMIC, AND IMMUNOGENICITY ANALYSES

4.1 EFFICACY AND QUALITY OF LIFE

All efficacy endpoints are secondary endpoints in this OLE study and will be evaluated descriptively.

4.1.1 *Available data*

Investigators report the participant's best disease status in episodes with start and end date (no CDA, CDA, CR, PR, Relapse and Treatment failure). Furthermore, BPDAI activity and total score, IGA-BP scores and itch NRS are collected over time.

Quality of life is assessed over time using the ABQOL, DLQI and EQ-5D-5L questionnaires.

The health impact of long-term glucocorticoid use is assessed via the Aggregate Improvement Score (AIS) and Cumulative Worsening Score from the Glucocorticoid Toxicity Index (GTI) and via the GTI Specific List (GTI-SL).

4.1.2 *Derivation rules*

The following endpoints will be derived **for each treatment period separately**:

- 1) Participants achieving CR while off OCS for ≥ 8 weeks (CROff). A participant will be considered a CROff responder if the following criteria are met simultaneously for ≥ 8 weeks (56 days):
 - The participant's reported disease status is CR
 - The participant is off OCS therapy
 - The participant does not receive any rescue therapy (as indicated by the investigator on the eCRF)

Else, the participant will be considered a CROff non-responder. Participants who already have the disease status CR at day 1 of the treatment period or who are off OCS therapy at day 1 of the treatment period or who receive rescue therapy at day 1 of the treatment period, will be considered non-evaluable for this endpoint and will be excluded from this analysis for the corresponding treatment period.

Note: the rules for assessing the OCS dose on a given day are described in section 3.4.2. Similarly, these rules can be used to assess whether rescue therapy is received on a given day. Additionally for rescue therapy, a frequency of PRN (pro re nata, or 'as needed') will be interpreted as a dose of 1 time per week.

- 2) Participants achieving CR or PR while off OCS for ≥ 8 weeks (CR/PROff). A participant will be considered a CR/PROff responder if the following criteria are met simultaneously for ≥ 8 weeks (56 days):
 - The participant's reported disease status is CR or PR (continuously or alternately)
 - The participant is off OCS therapy
 - The participant does not receive any rescue therapy (as indicated by the investigator on the eCRF)

	Statistical Analysis Plan	

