Else, the participant will be considered a non-responder for CROff without IMP. Participants who enter the ARGX-113-2010 study under protocol version 3 (26 April 2024) or 4 (02 May 2024) will be considered non-evaluable for this endpoint. Furthermore, participants who were randomized to the placebo arm in the ARGX-113-2009 study and who enter the ARGX-113-2010 study in the observation phase, will be considered non-evaluable for this endpoint in the observation phase.

- 6) Participants achieving CR or PR while off both OCS and efgartigimod PH20 SC for ≥ 8 weeks (CR/PROff without IMP). A participant will be considered a

	Statistical Analysis Plan	
ARGX-113-2010	Final analysis	Final 1.0 of 29APR2025

responder for CR/PROff without IMP if the following criteria are met simultaneously for ≥ 8 weeks (56 days):

- The participant's reported disease status is CR or PR (continuously or alternately)
- The participant is off OCS therapy
- The participant is off IMP
- The participant does not receive any rescue therapy (as indicated by the investigator on the eCRF)

Else, the participant will be considered a non-responder for CR/PROff without IMP. A participant will be considered non-evaluable for this endpoint using the same rules as for CROff without IMP.

- 7) Duration of sustained remission will be calculated for participants achieving CR while off both OCS and efgartigimod PH20 SC for ≥ 8 weeks (i.e., responders for CROff without IMP) within a treatment period.
 - Start date of sustained remission is 1 week (7 days) after the last IMP administration in the treatment period
 - End date of sustained remission is:
 - the start date of first relapse after achieving CROff without IMP
 - the start date of a (next) treatment period
 - the start date of OCS therapy after achieving CROff without IMP
 - the start date of a rescue therapy after achieving CROff without IMP
 whichever comes first. If none of the above occurs, the participant will be censored at the end date of the study (end date of last phase).
 - Duration of sustained remission (in days) = end date - start date + 1
- 8) Relapse will be evaluated for participants having or achieving CDA, CR or PR during the treatment period (or observation phase). The evaluation period for relapse is till the end of the treatment period (or observation phase) in case a (next) treatment period starts, or else till the end of the study. Only the first relapse in a treatment period (or observation phase) will be considered.

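### Response and remission rules recognise only oral glucocorticoids and investigator-ticked rescue, so an unflagged prohibited systemic BP treatment can leave a participant counted as a responder

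*SAP*

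**What the plan says.** SAP 3.3.2 supplies the two treatment definitions that the efficacy rules use. The first is by class and route: "OCS therapy is defined as any record from any eCRF page with medication class = 'GLUCOCORTICOIDS' and route = 'ORAL'". The second is by tick box: "Rescue therapy is defined as any therapy that is indicated as rescue therapy by the investigator on the eCRF page".

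SAP 4.1.2 item 1 then says: "A participant will be considered a CROff responder if the following criteria are met simultaneously for ≥ 8 weeks (56 days)". The criteria are reported complete remission (CR), being off OCS, and: "The participant does not receive any rescue therapy (as indicated by the investigator on the eCRF)". Items 2, 3, 5 and 6 use the same treatment tests. CRmin has a dose threshold in place of zero OCS, and the two off-IMP endpoints also require being off IMP. Item 7 ends sustained remission at relapse, the next treatment period, the start of OCS, or "the start date of a rescue therapy after achieving CROff without IMP".

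Protocol 6.9 lists treatments that are "not permitted as of when the ICF has been signed through the completion of the EoTP visit or EDV". Among them is "Any systemic treatment for BP (eg, IV or intramuscular corticosteroids, systemic immunosuppressants) except OCS". Immunoglobulin (except IV immunoglobulin begun as rescue in ARGX-113-2009), plasma exchange, immunoadsorption, monoclonal antibodies, sulfasalazine and other systemic biologics are listed separately.

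The protocol speaks of rescue therapy only as something begun in ARGX-113-2009 (Definitions of Terms, 6.3, 6.9.2). Footnote a of protocol Table 4 says the response criteria can be met only off rescue; it does not mention prohibited therapy. The protocol defines no estimands (section 3) and no per-protocol set (9.2).

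**The concern.** Whether an added systemic BP drug disqualifies a response depends on how the record was ticked, not on the drug. An immunosuppressant carried over from ARGX-113-2009 and flagged breaks the 56-day run. The same drug newly started here and left unflagged does not. Under the protocol's usage a new drug of this kind is a prohibited medication, so the investigator has no stated basis in the protocol for calling it rescue.

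The error has one direction. Effective treatment added during the study can produce or prolong CR, and the rule then credits that remission to efgartigimod. There is no control arm in which the same error could occur. Prohibited use would appear in the protocol-deviation table (SAP 3.1) and the concomitant-therapy tables (SAP 3.3.3), but neither display feeds into response status.

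**Working it through.** The plan has no figure to reproduce: the study is descriptive, with no hypothesis test and no powered sample size. The check applies the rule as written to constructed records.

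**Rule.** A day counts if status is CR, no record with class glucocorticoid and route oral covers it, and no investigator-flagged rescue covers it. A run of at least 56 counting days makes a CROff responder.

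**Constructed participant.** Not in CR on day 1, on oral prednisone through day 59, CR reported on days 60 to 330, and a second drug recorded on days 60 to 330. All of this lies within 48 weeks (48 × 7 = 336 days). The longest possible run is 330 − 60 + 1 = 271 days.

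| Second drug | Run under SAP rule | Run if any systemic BP drug also disqualifies |
|---|---|---|
| None | 271, responder | 271, responder |
| IM or IV steroid, unflagged | 271, responder | 0, non-responder |
| Immunosuppressant, unflagged | 271, responder | 0, non-responder |
| Monoclonal antibody, unflagged | 271, responder | 0, non-responder |
| Immunosuppressant, flagged | 0, non-responder | 0, non-responder |
| Oral prednisone | 0, non-responder | 0, non-responder |

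The SAP rule cannot tell the three unflagged cases from a participant on no added drug.

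**Size per case.** One participant wrongly counted among n evaluable raises the proportion by 100/n points:

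- n = 20: 100/20 = 5.0
- n = 30: 100/30 = 3.3
- n = 50: 100/50 = 2.0
- n = 70: 100/70 = 1.4
- n = 100: 100/100 = 1.0

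These n are assumptions. The documents give neither the evaluable number nor the frequency of prohibited use.

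**Sustained remission.** The protocol's Definitions of Terms require the participant to be off concurrent BP therapy. That term means any therapy given in this study for BP other than efgartigimod; rescue, OCS and topical steroids are named as what it may include. A new IV steroid or immunosuppressant given for BP fits that definition. Item 7 has no end date for it unless it is flagged, so item 7 is narrower than the protocol definition.

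**Follow-up.** The prohibition stops at EoTP or EDV, while item 7 censors at the end of the last phase. In the follow-up period (8 of 56 weeks, 8/56 = 14.3%) a new non-oral, unflagged systemic drug would be neither a deviation under 6.9 nor an end to remission. This affects item 7 only. Items 1 to 3 are derived within treatment periods, which end at week 48 or EDV (SAP Table 2).

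**The case against.** The best reply is that the SAP's flag has no origin restriction. It covers any therapy the investigator marks, and item 7 plainly expects rescue to start during this study. Sites may have been told to tick prohibited BP drugs as rescue; the eCRF completion guidance (protocol 10.1.8) is not among the documents. This stands. A reader might infer that newly started drugs can never be caught, and the documents do not support that. They show that capture depends on a tick for which the protocol gives no rule.

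The SAP also follows the protocol's endpoint footnote, so for the response proportions the gap begins in the protocol and is not an SAP departure. This stands for items 1-3, 5 and 6, but not for item 7.

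A participant on a prohibited drug may not stay on treatment either. Protocol 7.1.1 allows IMP to be stopped in the participant's best interest, and 7.2 allows withdrawal for noncompliance. Both are discretionary and neither changes how a response already reached is counted.

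Finally, where a relapse prompts the drug, the relapse comes first and already counts in items 7 to 9. That is right, and it leaves use for activity short of relapse and pre-emptive use. Item 7 also reaches few people, because participants entering under protocol version 3 or 4 are non-evaluable for the endpoint on which it depends.

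**Conclusion.** The gap is real and its direction is clear: under the rules as written, an unflagged prohibited systemic BP treatment does not prevent a response and does not end sustained remission. The effect is 100/n points per case, or 1 to 5 points for an assumed evaluable n of 100 to 20. It requires that the drug is unflagged, that CR (or PR, where allowed) is reported for 56 days with the OCS criterion met, and that the participant has no other qualifying run.

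Three stronger inferences are not supported:

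- A total overstatement. For example, assuming 4 such cases among 30 evaluable would give 4/30 = 13.3 points, but nothing in the documents supports either count.
- That follow-up has no rule for new therapy. OCS and flagged rescue already end sustained remission to the end of the last phase.
- That these proportions are the only efficacy evidence. BPDAI, IGA-BP, itch, relapse and treatment failure are also reported, and all efficacy endpoints are secondary and descriptive.

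**What to change.** In SAP 3.3.2, derive a flag for non-permitted systemic BP therapy from coded drug class, route and BP indication, whatever the rescue tick box says. Match it to the full protocol 6.9 list, including sulfasalazine and the procedures (plasma exchange, immunoadsorption).

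In SAP 4.1.2, treat the flag exactly as rescue therapy in items 1-3, 5 and 6. Use on day 1 of a treatment period would then make the participant non-evaluable for items 1-3, as rescue does. In item 7, add its start as an end date, including during follow-up. State how long a single administration counts: a one-day record would otherwise break the run only on that day.

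Do not add censoring to time to relapse (item 9). Item 9 censors at neither OCS nor rescue, so censoring at prohibited therapy alone would be inconsistent. It would also be informative, because the drug is likely to be started when control is failing. If wanted, report a sensitivity analysis in which the start of any added systemic BP therapy counts as an event.

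The cost is SAP wording and a little programming. Dates and reason for use (protocol 6.9) and ATC coding and procedure terms with indication (SAP 3.3.1) are already collected. Response proportions may come out slightly lower.

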3.3.3 Presentation of results

Concomitant therapies will be tabulated by ATC class (level 1 and 3) and generic term. Tables will be presented per phase and within the treatment phase data will be summarized overall and per subperiod.

Separate tables will be created for the number and percentage of participants with:

- Concomitant therapies, excluding OCS, TCS and rescue therapies
- Concomitant OCS therapies
- Concomitant TCS therapies
- Concomitant rescue therapies

Displays will be based on the ROL analysis set. All concomitant therapies data will be listed with detailed information about ATC classes.

3.4 EXPOSURE TO IMP AND OCS

3.4.1 Available data

For each IMP administration and OCS administration, the start and end date, doses (per administration), dose units and the volume with units (for IMP only) will be recorded.

	Statistical Analysis Plan	
ARGX-113-2010	Final analysis	Final 1.0 of 29APR2025

3.4.2 *Derivation rules*

The total number of IMP administrations in the study will be derived as the sum of all administrations of IMP.

OCS is defined in section 3.3.2. OCS dose (mg) and OCS dose per body weight (mg/kg) will be calculated for each day in the study and will be based on prednisone equivalent dose.

Prednisone equivalent dose is calculated as [dose of ATC]*[equivalence factor prednisone]/[equivalence factor ATC]. Following [equivalence factors] are used:

- Betamethasone [1.5]
- Cortisone [37.5]
- Deflazacort [15]
- Dexamethasone [1.5]
- Fluocortolone [10]
- Hydrocortisone [30]
- Hydrocortisone sodium phosphate [30]
- Methylprednisolone [8]
- Methylprednisolone acetate [8]
- Methylprednisolone sodium succinate [8]
- Paramethasone [4]
- Prednisolone [10]
- Prednisone [10]
- Prednisolone acetate [10]
- Prednisone acetate [10]
- Prednisolone sodium succinate [10]
- Prednylidene [12]
- Rimexolone [20]
- Triamcinolone [8]

Example: calculation of equivalent dosage of 12 mg methylprednisolone: $12 * 10 / 8 = 15$ mg prednisone.

Following rules will be applied to calculate the daily OCS dose (per body weight):

- Records with (partially) missing dates will be imputed as detailed in section 2.3.2.
- If dates of administration records overlap, the overlapping reported doses will be added together.

	Statistical Analysis Plan	
ARGX-113-2010	Final analysis	Final 1.0 of 29APR2025

- If for a given day, no record exists in the eCRF indicating OCS use that day, the dose will be assumed to be 0 mg.
- If an administration is reported as dose per administration with frequency, then the doses should be allocated to the correct dates, taking the start date and the frequency into account.

Example:

- Dose: 40 mg
- Frequency: every other day
- Start - Stop date: 01JAN2022 - 03JAN2022

This will result in:

- 40 mg be allocated to 01JAN2022
- 0 mg allocated to 02JAN2022
- 40 mg allocated to 03JAN2022
- OCS dose per body weight will be calculated based on the most recent assessment of body weight available for a study day.

3.4.3 *Presentation of results*

Exposure information will be presented using descriptive statistics for the total number of IMP administrations, based on the SAF analysis set.

OCS dose (per body weight) at study baseline will be included in the tabulation of baseline disease characteristics, based on the ROL analysis set.

All exposure data to IMP and OCS will be listed.

	Statistical Analysis Plan	
ARGX-113-2010	Final analysis	Final 1.0 of 29APR2025

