8.2.1. Efficacy Measures

8.2.1.1. Assessment of BP Disease Status and OCS Dose Monitoring

The BP disease status will be assessed by the investigator at on-site visits according to the definitions/criteria presented in the [Definitions of Terms](#). During these visits, the investigator will examine the participant for new lesions (transient or nontransient), record the daily concurrent BP therapy (if applicable) administered to the participant since the last visit, including the dose, adjust the daily OCS dose (taper, stop, reinstate, or increase; if applicable) based on the participant's BP disease status, and record treatment failure.

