2.3.2 Handling partially or completely missing dates in calculations

OCS administration start dates with partially missing data will be imputed as follows:

- Missing day will be imputed with first day of the month or start date of the first phase, whichever comes latest.
- Missing day and month will be imputed with 1JAN or start date of the first phase, whichever comes latest.
- Completely missing date will be imputed with start date of the first phase.

	Statistical Analysis Plan	
ARGX-113-2010	Final analysis	Final 1.0 of 29APR2025

OCS administration end dates with partially missing data will be imputed as follows:

- Missing day will be imputed with the last day of the month or the end date of the last phase, whichever comes first.
- Missing day and month will be imputed with 31DEC or the end date of the last phase, whichever comes first.
- Completely missing end date will be imputed with the end date of the last phase.

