ARGX-113-2010	Final analysis	Final 1.0 of 29APR2025

Else, the participant will be considered a CR/PROff non-responder. Participants who already have the disease status CR or PR at day 1 of the treatment period or who are off OCS therapy at day 1 of the treatment period or who receive rescue therapy at day 1 of the treatment period, will be considered non-evaluable for this endpoint and will be excluded from this analysis for the corresponding treatment period.

- 3) Participants achieving CR while on minimal OCS therapy for ≥ 8 weeks (CRmin). A participant will be considered a CRmin responder if the following criteria are met simultaneously for ≥ 8 weeks (56 days):
- The participant's reported disease status is CR
 - The participant receives ≤ 0.10 mg/kg/day of prednisone (or an equivalent dose of another OCS)
 - The participant does not receive any rescue therapy (as indicated by the investigator on the eCRF). OCS used as rescue therapy will not be considered as rescue therapy if the above criterium of minimal OCS therapy is still met.

Else, the participant will be considered a CRmin non-responder. Participants who already have the disease status CR at day 1 of the treatment period or who are on minimal (≤ 0.10 mg/kg/day) OCS therapy at day 1 of the treatment period or who receive rescue therapy at day 1 of the treatment period, will be considered non-evaluable for this endpoint and will be excluded from this analysis for the corresponding treatment period.

- 4) Participants with treatment failure.

The following endpoints will be derived **for each treatment period separately and additionally for the observation phase:**

- 5) Participants achieving CR while off both OCS and efgartigimod PH20 SC for ≥ 8 weeks (CROff without IMP). A participant will be considered a responder for CROff without IMP if the following criteria are met simultaneously for ≥ 8 weeks (56 days):
- The participant's reported disease status is CR
 - The participant is off OCS therapy
 - The participant is off IMP
 - The participant does not receive any rescue therapy (as indicated by the investigator on the eCRF)

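### The OCS daily-dose rules can add successive taper steps together, giving a dose nobody took and, under stated conditions, false breaks in the remission endpoints

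*SAP*

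**What the plan says.** SAP 3.4.2 derives an OCS dose for every study day. Where records coincide, "If dates of administration records overlap, the overlapping reported doses will be added together". The worked example in the same section, a record running from 1 to 3 January, has "40 mg allocated to 03JAN2022", so the stop date is a dosing day.

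SAP 2.3.2 imputes incomplete OCS end dates. For a partial date: "Missing day will be imputed with the last day of the month or the end date of the last phase, whichever comes first". For an absent one: "Completely missing end date will be imputed with the end date of the last phase". An absent start date goes back to the start of the first phase. Neither section shortens a record because a later one begins, and neither separates a taper transition from concurrent dosing.

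The derived dose feeds several results. In SAP 4.1.2 the CRmin rule reads "A participant will be considered a CRmin responder if the following criteria are met simultaneously for ≥ 8 weeks (56 days", with no tolerance day; the dose criterion is at most 0.10 mg/kg/day. CROff and CR/PROff need 56 days off OCS. CRmin evaluability depends on the dose on day 1 of the treatment period. The baseline OCS dose is the only OCS dose summarised in a table (SAP 3.4.3).

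Protocol 8.2.1.1 has the investigator "adjust the daily OCS dose (taper, stop, reinstate, or increase; if applicable" at visits. Protocol 8.1 puts the baseline visit on the same day as the parent study's last treatment visit.

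**The concern.** OCS tapering produces a chain of records, each replacing the one before. Summing is right for records taken together, such as two tablet strengths making up one daily dose. It is wrong for records that follow one another. If the old step ends on the date the new one starts, that day carries both doses. If a completed step has no end date, it runs on under every later step.

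The remission endpoints need unbroken 56-day runs, so one false day can restart a run, and one record left open can prevent an off-OCS run altogether. An overlap on study day 1 misstates the tabulated baseline dose.

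**Working it through.** **Inputs.** The overlap rule and inclusive stop date are from SAP 3.4.2, the imputation from SAP 2.3.2, and the 56-day runs from SAP 4.1.2. Doses within the minimal band are from Protocol Table 6:
- 45 to <50 kg: 2.5 mg
- 50 to <75 kg: 5, 2.5 mg
- 75 to <100 kg: 7.5, 5, 2.5 mg
- 100 to <110 kg: 10, 7.5, 5, 2.5 mg

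The two outer columns of Table 6 give only recommended bounds and are left out, which leaves 13 columns.

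**Assumptions.** Steps of 14 days (the longest that Table 6's note allows), CR throughout, day 1 = first day at the minimal dose, 0 mg counts as at most 0.10 mg/kg, whole-kilogram weights, 48 weeks (336 days).

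**Reproducing the SAP's examples.** 12 mg methylprednisolone × 10/8 = 15 mg prednisone. 40 mg every other day over three days gives 40, 0, 40 mg. Both agree with the SAP.

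**1. Which shared dates exceed 0.10 mg/kg?** Summed dose ÷ weight:

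| Step (mg) | Sum (mg) | Weight (kg) | mg/kg | Breaks the run? |
|---|---|---|---|---|
| 5 to 2.5 | 7.5 | 50–74 | 0.101–0.150 | Yes |
| 5 to 2.5 | 7.5 | 75–109 | 0.069–0.100 | No |
| 7.5 to 5 | 12.5 | 75–109 | 0.115–0.167 | Yes |
| 10 to 7.5 | 17.5 | 100–109 | 0.161–0.175 | Yes |

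The 45 to <50 kg column has no step within the band. At least one false break is possible in 12 of 13 columns.

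**2. Delay to CRmin with shared dates.** Let s be the step length and k the number of the last breaking transition. The summed day is ks + 1, the run restarts on day ks + 2 and completes on day ks + 57 instead of day 56. The delay is ks + 1.
- 50 to <100 kg (k = 1): day 71, delay 15 days.
- 100 to <110 kg (k = 2): day 85, delay 29 days.
- With 7-day steps the delays are 8 and 15 days.

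**3. Effect on the yes/no result.** A true run of L days is lost if L ≥ 56 but L − (ks + 1) < 56. With 14-day steps that is L = 56–70 at 50 to <100 kg and L = 56–84 at 100 to <110 kg. If 0 mg were not counted as minimal therapy, the in-band steps would total 14, 28, 42 or 56 days. Only 100 to <110 kg would then reach 56 days, and shared dates would break that run.

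**4. First in-band step with a completely missing end date.** At 77 kg the 7.5 mg record runs on. Days 15–28 become 12.5 mg (0.162 mg/kg), days 29–42 become 10 mg (0.130), then 7.5 mg (0.097). The CRmin run is days 43–98. By column, day of completion:

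| Weight (kg) | CRmin, true | CRmin, as written | 56 days off OCS, true | 56 days off OCS, as written |
|---|---|---|---|---|
| 45–<50 | 56 | 56 | 70 | never |
| 50–<75 | 56 | 84 | 84 | never |
| 75–<100 | 56 | 98 | 98 | never |
| 100–<110 | 56 | 112 | 112 | never |

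If only the day is missing, the extension stops at month end.

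**5. Overlap on study day 1.** At 77 kg, a step from 22.5 to 15 mg with both records covering day 1 gives 37.5 mg (0.49 mg/kg) instead of 15–22.5 mg (0.19–0.29). At 75 kg, 10 + 7.5 = 17.5 mg gives 0.233 instead of 0.10 mg/kg at the new step. If that is also day 1 of the treatment period, a participant on minimal OCS would not be excluded from CRmin on that ground. Between adjacent mg/kg levels of Table 6, the sum is 2.2 to 3.0 times the new step's dose.

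**The case against.** The strongest reply is that the trigger lies outside the documents. If stop dates are dosing days, a cleanly entered taper step ends the day before the next begins and nothing overlaps. Entry guidance is in an eCRF completion document that is not supplied (Protocol 10.1.8). End dates are to be recorded, the data are quality-checked, and OCS records are listed. All of this stands: the frequency of shared or missing dates cannot be found here and could be zero.

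A second reply is that CRmin is tabulated as achieved at least once, and time to CRmin is not analysed. In the shared-date calculation above, with 0 mg counted, every modelled participant still meets CRmin within 48 weeks. This also stands. A reader might infer that shared dates routinely cost participants their CRmin response; the documents support a delay, and a loss only for short qualifying runs.

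A third reply is that running an open record to the end of the last phase is correct for ongoing OCS, and that summing is correct for two tablet strengths. Agreed: the gap is the missing rule for superseded records. For the same reason, a blanket cap at the next record of the same drug would be wrong. It could cut off a continuing record when a second strength is added, and it would miss a switch between OCS drugs.

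None of these replies supplies a rule that stops successive steps from being summed when dates do coincide or are missing.

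**Conclusion.** The point holds conditionally. As written, SAP 3.4.2 and 2.3.2 give a false daily dose whenever successive OCS records share a date or a completed step lacks an end date.

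Under the 14-day-step assumptions, shared dates delay CRmin by 15 or 29 days. They do not break the run for 5 to 2.5 mg at 75 kg or more, or at 45 to <50 kg. A completely missing end date on a completed step has the larger effect, because CROff and CR/PROff cannot be met after that step starts.

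A reader might also infer that the baseline dose is overstated for everyone whose OCS is changed at rollover. The documents do not support that: it is wrong only for participants whose records overlap on study day 1, and their number is unknown.

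The results at risk are descriptive secondary endpoints and one baseline summary. No hypothesis is tested and the primary safety endpoints do not use this dose. False breaks understate remission; a false day-1 dose can also wrongly add someone to the CRmin denominator.

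**What to change.** - **SAP 2.3.2:** when a later OCS record supersedes a record with a missing end date (a changed dose in the same OCS course, including a switch of OCS drug), cap the imputed end date at the day before the later record starts.
- **SAP 3.4.2:** on a date shared by two successive steps, use only the new step's dose. Keep summing records with known dates that overlap by more than the single transition day, and records that data review or query confirms as concurrent, such as two tablet strengths.

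The cost is two SAP sentences, a small programming change and a review of flagged overlaps before database lock. If there are no such overlaps, no result changes.
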